1 PROTOCOL SUMMARY

1.1 Synopsis

Background and Rationale:

This study will investigate the efficacy of an experimental dentifrice, containing 0.454% stannous fluoride and 0.3% zinc chloride, to reduce oral malodor, compared to a marketed regular fluoride dentifrice after 3 weeks twice daily brushing in a population of clinically diagnosed gingivitis. Oral malodor will be evaluated using a hedonic scale assessed by a panel of calibrated organoleptic assessors who will sniff the subject's breath, and through the instrumental measurement of the concentration of volatile sulfur compounds (VSCs) of a sample of the subject's breath.

Objectives and Endpoints:

Objectives	Endpoints
Primary	
To evaluate and compare the change in morning oral malodor by an organoleptic assessment following 3 weeks of twice-daily tooth brushing using an experimental dentifrice containing 0.454% stannous fluoride and 0.3% zinc chloride compared to a standard fluoride dentifrice.	Change in mean organoleptic score from Baseline (pre-brushing) to 3 weeks (pre-brushing)
Secondary	
To evaluate and compare the change in morning oral malodor by VSC determination following 3 weeks of twice-daily tooth brushing using an experimental dentifrice containing 0.454% stannous fluoride and 0.3% zinc chloride compared to a standard fluoride dentifrice.	Change from Baseline (pre-brushing) to 3 weeks (pre-brushing) in:- 
Mean total VSC concentration in breath.Mean hydrogen sulfide, methanethiol and dimethyl sulfide concentration in breath.
To evaluate and compare the change in oral malodor post brushing following 3 weeks of twice-daily tooth brushing using an experimental dentifrice containing 0.454% stannous fluoride and 0.3% zinc chloride compared to a standard fluoride dentifrice.	Change from Baseline (pre-brushing) to 3 weeks (1 hour post-brushing) in: 
Mean total VSC concentration in breath.Mean hydrogen sulfide, methanethiol and dimethyl sulfide concentration in breath.Mean breath organoleptic scores.
To evaluate and compare the change in oral malodor 1 hour post brushing at Baseline, and 1 hour post brushing following 3 weeks twice-daily use using an experimental dentifrice containing 0.454% stannous fluoride and 0.3% zinc chloride compared to a standard fluoride dentifrice.	Change from pre-brushing to 1 hour post brushing at Baseline and after 3 weeks in:- 
Mean total VSC concentration in breath.Mean hydrogen sulfide, methanethiol and dimethyl sulfide concentration in breath.Mean breath organoleptic scores.
Safety	
To assess the tolerability of an experimental dentifrice containing 0.454% stannous fluoride and 0.3% zinc chloride	Treatment emergent adverse events

Study Design:

This will be a single center, single blind (to the examiners undertaking the oral malodor assessments), randomized (stratified by subject's sex), controlled, two arm parallel study in volunteers with clinically diagnosed gingivitis. The study will evaluate the clinical efficacy of an experimental dentifrice containing 0.454% stannous fluoride and 0.3% zinc chloride to reduce oral malodor after 3 weeks of twice-daily use compared to a regular reference dentifrice.

Potential subjects will attend a screening visit to determine their suitability to participate. Having obtained their written informed consent, relevant details of their medical history and current medications will be recorded. Subjects will then undergo the screening assessment of their oral malodor followed by oral soft tissue (OST) and oral hard tissue (OHT) examinations and an assessments of gingivitis (Bleeding on probing examination). Subjects with gingivitis and oral malodor per the inclusion criteria, as well as meeting all other study criteria, will be considered as eligible to proceed, appointed for baseline assessments and dispensed a washout dentifrice and toothbrush to use instead of their regular oral hygiene products until they return for Visit 2 (1-3 weeks after screening).

At the Baseline visit (Visit 2), subjects, having abstained from oral hygiene procedures and food consumption for at least 8 hours, will undergo baseline breath VSC and organoleptic assessments. Qualifying subjects will be stratified by the subject's sex and randomized to one of the two study treatments. Subjects will then be instructed on the use of their study products and will brush their teeth, under supervision, for 1 minute with their assigned dentifrice. One hour (± 5 minutes) post brushing, subjects will have their post-brushing breath VSC and organoleptic assessments. Subjects will then undergo an OST examination and instructed to brush twice daily (for 1 minute, morning and evening) with their assigned study dentifrice for the next 3 weeks until their next visit (Visit 3).

At Visit 3, subjects, having abstained from oral hygiene procedures and food consumption for at least 8 hours will undergo pre- and post-brushing evaluation of breath VSCs and organoleptic scores in the same manner as performed at the Baseline visit. Subjects will then undergo OST and OHT examinations and exit the study.

Study Products:

Experimental Dentifrice	Reference Dentifrice
Dentifrice containing 0.454% stannous fluoride and 0.3% zinc chloride.	Standard Fluoride Dentifrice [0.243% sodium fluoride] (Crest Cavity Protection, US market)

Both dentifrices will be brushed on to the teeth, twice daily (morning and evening) for 1 timed minute in line with the usage instructions in [Appendix 15.1](#).

Type and Planned Number of Subjects:

Study subjects of either sex and any gender, aged of 18-65 years, will be in good general health with clinically diagnosed gingivitis and with the level of oral malodor required at baseline to participate in the study.

Sufficient subjects will be screened to randomize approximately 106 subjects to study treatment (approximately 53 per treatment group) to ensure approximately 100 evaluable subjects complete the study.

Statistical Analysis:

For the primary endpoint analyses, an ANCOVA model will be used to analyze the change in mean breath organoleptic score from Baseline (pre-brushing) to 3 weeks (pre-brushing) with study product and gender as fixed effects and the mean Baseline (pre-brushing) breath organoleptic score as a covariate. The difference between least square means for the Experimental Dentifrice compared to the Reference Dentifrice will be used to test for a difference between products at the two-sided 5% significance level. The assumption of normality and homogeneity of variance in the ANCOVA will be investigated. In case of violation of these assumptions, a suitable nonparametric test (adjusted for gender) will be performed, and results will be provided to support the ANCOVA results.

For secondary endpoint change from Baseline analyses, a similar ANCOVA model as used for the primary analysis will be applied but with the appropriate pre-brushing and post-baseline result used accordingly. For VSC endpoints, data will be log (base 10) transformed prior to analysis. There will be no adjustment for multiplicity for secondary endpoints.

1.2 Schedule of Activities

The schedule of activities table provides an overview of the subject visits and study procedures.

The investigator may schedule visits (unplanned visits) in addition to those listed on the schedule of activities, to conduct evaluations or assessments required to protect the well-being of the subject.

Table 1-1 Schedule of Activities

Procedure/Assessment	Screening	Study Period	
	Visit 1	Visit 2 Baseline	Visit 3 Week 3
Informed consent	X		
Demographics	X		
Medical history	X		
Current/prior/concomitant medication review	X	X	X
Screening assessment of oral malodor	X		
OST examination	X	X	X
OHT examination	X		X
Bleeding on probing assessment	X		
Review of inclusion/exclusion criteria	X	X	
Subject eligibility	X	X	
Dispense wash-out dentifrice, toothbrush and washout diary	X		
Subject returns wash-out dentifrice and toothbrush and washout diary		X	
Pre-brushing assessment of oral malodor ²		X	X
Subject continuance			X
Stratification and randomization		X	
Dispense study products, subject diary and sundry items with instruction in proper use		X	
Supervised brushing		X	X
Post-brushing assessment of oral malodor ³		X	X
Return study products and subject diary			X
Adverse events review ¹	X	X	X
Medical device incidents review ¹		X	X
Study conclusion			X

Abbreviations: OST: Oral Soft Tissue, OHT: Oral Hard Tissue, VSC: Volatile Sulfur Compound

Footnotes:

1. Adverse Events (AEs), Serious Adverse Events (SAEs) and medical device incidents collected immediately after subject provides consent to participate in the study by the completion of the Informed Consent Form (ICF). Medical device in this study is the supplied toothbrush.
2. At Visits 2&3, pre-brushing breath VSC-determination (by OralChroma) and organoleptic assessments will be performed with subjects having not brushed their teeth and not eaten for at least 8 hours.
3. Post-brushing breath VSC-determination (by OralChroma) and organoleptic assessments will be performed 1 hour (± 5 minutes) after supervised brushing.

2 INTRODUCTION

It is generally accepted that oral malodor primarily originates from bacterial putrefaction of proteinaceous and other compounds within the oral cavity particularly by anaerobic bacteria including *Bacteroides forsythus*, *Actinobacillus actinomycetemcomitans* and *Prevotella intermedia* ([Awano et al., 2002](#)). These bacteria are located throughout the oral cavity, and are found in particularly high numbers in saliva ([Awano et al., 2002](#)) and on the tongue, especially towards the tongue posterior ([Allaker et al., 2008](#)). These bacterial species are also associated and present in higher numbers in those with gingivitis and periodontal disease ([Abusleme et al., 2021](#))

The odors that these bacteria produce include amines such as putrescine and cadaverine and fatty acids such as butyrate and valerate ([Van den Broek et al., 2007](#)). However, a significant contributor to oral malodor are the volatile sulfur compounds (VSCs) such as hydrogen sulfide, methanethiol and dimethyl sulfide, with hydrogen sulfide the most concentrated odor on the breath of oral malodor sufferers ([Washio et al., 2005](#)).

Although management of oral malodor is an active area of research, objective, clinical measurement of oral malodor, and thereby determination of the efficacy of condition management, is currently not possible. Organoleptic/hedonic assessment is often employed and clearly has the benefit of simplicity and relevancy to patients, however the human nose is not linear in response to malodor concentration and measurement is often complicated by the flavors that are routinely added to healthcare products. Measurement of VSC concentration in breath is therefore routinely used as a quantifiable surrogate measurement and given the prevalence of VSCs in breath this would appear to be appropriate. Indeed, clinical measurement of VSCs by techniques such as the Halimeter, the OralChroma and gas chromatography (GC) have been used to provide clinical evidence of efficacy of treatments ([Vandekerckhove et al., 2009](#), [Oho et al., 2001](#)). Moreover, Rosenberg *et al.* have demonstrated a correlation between organoleptic assessment of oral malodor and clinically measured VSC concentrations ([Rosenberg et al., 1991a](#)).

Whilst not yet conclusive, there is evidence that periodontal diseases may be a factor in the etiology of oral malodor ([De Geest et al., 2016](#)). Oral malodor has been significantly related to periodontal pocket depth ([Chen et al., 2016](#)) and analysis of periodontal pockets has shown the presence of high concentrations of VSCs ([Rizzo, 1967](#)). Additionally the bacterial species associated with gingivitis and periodontal disease are also implicated in oral malodor ([Abusleme et al., 2021](#)).

Effective treatments to control oral malodor include mechanical removal of oral bacteria and dental plaque, such as tongue scraping and tongue/tooth brushing, and adjunctive use of antimicrobials such as chlorhexidine, cetylpyridinium chloride, essential oils and zinc ions ([De Geest et al., 2016](#)).

This study aims to assess the oral malodor of subjects with clinically diagnosed gingivitis who use an experimental dentifrice containing both stannous fluoride and zinc ions compared to use of a standard sodium fluoride dentifrice.

2.1 Study Rationale

This 3-week, randomized, controlled, parallel-design, stratified clinical study has been designed to evaluate the ability of an experimental dentifrice containing 0.454% stannous fluoride and 0.3% zinc chloride to reduce oral malodor, compared to a regular fluoride dentifrice in a population with clinically diagnosed gingivitis.

Property of GSK Consumer Healthcare - Confidential

May not be used, divulged, published or otherwise disclosed without the consent of GSKCH

The anti-gingivitis benefits of stannous fluoride dentifrices similar to the test product is well established (see [Section 2.2](#)). Additionally, the oral malodor benefits through use of a single application of zinc-containing dentifrices has also been demonstrated in a non-gingivitis population. However, additional data are required to confirm the oral malodor reduction benefit of the experimental dentifrice in a population of subjects with clinically diagnosed gingivitis. The study will inform on the efficacy of the experimental dentifrice to reduce oral malodor through usage over 3 weeks (in line with ADA guidelines for the testing of products used in the management of oral malodor ([ADA, 2016](#))).

2.2 Background

The experimental dentifrice being tested contains stannous fluoride, an active with an extensive history of gum-health efficacy ([Makin, 2013](#), [Paraskevas and Van der Weijden, 2006](#), [Twetman et al., 2003](#), [Rølla and Ellingsen, 1994](#)). Formulations containing the same concentration of stannous fluoride as in the experimental dentifrice being evaluated in this study (although not containing zinc ions), have been evaluated previously both for dentine hypersensitivity relief ([Parkinson et al., 2013](#), [Parkinson et al., 2015](#), [Parkinson et al., 2016](#)) and improvements in gingivitis ([Parkinson et al., 2018b](#), [Parkinson et al., 2018a](#)). Additionally this formulation has been shown not to exhibit dental staining that has previously been observed with stannous fluoride-based dentifrices ([Nehme et al., 2013](#)). Stannous fluoride has been recognized as safe and effective for the treatment of gingivitis by the US Food and Drug Administration (FDA) ([FDA, 2003](#)). Additionally a 0.45% stannous fluoride dentifrice has been shown to reduce oral malodor using both VSC measurement and organoleptic assessment in a non-gingivitis healthy population ([Gerlach et al., 1998](#)).

Given the association between gum disease and oral malodor (see Introduction) it is expected that treatment of gingivitis (through stannous fluoride) will additionally show benefits in oral malodor. Additionally, zinc-containing products are highly effective at reducing oral malodor ([Young et al., 2001](#), [Schmidt and Tarbet, 1978](#), [Newby et al., 2008](#), [Payne et al., 2011](#)), possibly because they are dual active, being both antimicrobial, and chemically reactive to VSCs resulting in non-volatile (and therefore non-odorous) sulfur species ([Burnett et al., 2011](#)).

In summary, existing clinical data provide evidence of oral malodor efficacy for zinc-containing dentifrice formulations. However there appears to be little published evidence on the efficacy of these formulations for those with gingivitis. This study will therefore evaluate the efficacy of an experimental dentifrice containing stannous fluoride and zinc chloride in reducing oral malodor in a population of subjects with clinically diagnosed gingivitis.

2.3 Benefit/Risk Assessment

Complete information for the experimental dentifrices may be found in the single reference safety document (SRSD), which for this study is the Safety Statement.

Whilst the exact formulation of the experimental dentifrice under investigation has not been previously clinically tested, similar products containing stannous fluoride and zinc chloride have been evaluated in clinical studies (see [Background Section 2.2](#)). These studies demonstrated the anti-gingivitis and/or anti oral malodor efficacy and safety of similar formulations. The active ingredients and formulation excipients contained in the study dentifrices have a history of safe use in oral care products and are currently used in marketed daily use dentifrices.

The experimental dentifrice is considered generally safe for topical oral use, with twice daily brushing, under the controlled conditions of a clinical trial.

2.4 Mechanism of Action/Indication

This study will be conducted in generally healthy subjects with clinically diagnosed gingivitis and with a minimum level of clinically-measured oral malodor as described in the inclusion criteria. The dentifrice being evaluated contains zinc ions which are effective at reducing oral malodor through their antimicrobial activity coupled with their ability to chemically react with VSCs resulting in non-volatile (and therefore non-odorous) sulfur species ([Burnett et al., 2011](#)). Additionally, the stannous fluoride in the formulation is expected to provide oral malodor benefits through its antimicrobial/ antiplaque benefits ([Bosma et al., 1997](#), [Mankodi et al., 2005](#), [Mallatt et al., 2007](#)) leading to improvements in gingivitis ([Parkinson et al., 2018a](#), [Parkinson et al., 2018b](#)).

3 STUDY OBJECTIVES AND ENDPOINTS

Table 3-1 Study Objectives and Endpoints

Objectives	Endpoints
Primary	
To evaluate and compare the change in morning oral malodor by an organoleptic assessment following 3 weeks of twice-daily tooth brushing using an experimental dentifrice containing 0.454% stannous fluoride and 0.3% zinc chloride compared to a standard fluoride dentifrice.	Change in mean organoleptic score from Baseline (pre-brushing) to 3 weeks (pre-brushing)
Secondary	
To evaluate and compare the change in morning oral malodor by VSC determination following 3 weeks of twice-daily tooth brushing using an experimental dentifrice containing 0.454% stannous fluoride and 0.3% zinc chloride compared to a standard fluoride dentifrice.	Change from Baseline (pre-brushing) to 3 weeks (pre-brushing) in:- 
 Mean total VSC concentration in breath. Mean hydrogen sulfide, methanethiol and dimethyl sulfide concentration in breath.
To evaluate and compare the change in oral malodor post brushing following 3 weeks of twice-daily tooth brushing using an experimental dentifrice containing 0.454% stannous fluoride and 0.3% zinc chloride compared to a standard fluoride dentifrice.	Change from Baseline (pre-brushing) to 3 weeks (1 hour post-brushing) in: 
 Mean total VSC concentration in breath. Mean hydrogen sulfide, methanethiol and dimethyl sulfide concentration in breath. Mean breath organoleptic scores.
To evaluate and compare the change in oral malodor 1 hour post brushing at Baseline, and 1 hour post brushing following 3 weeks twice-daily use using an experimental dentifrice containing 0.454% stannous fluoride and 0.3% zinc chloride compared to a standard fluoride dentifrice.	Change from pre-brushing to 1 hour post brushing at Baseline and after 3 weeks in:- 
 Mean total VSC concentration in breath. Mean hydrogen sulfide, methanethiol and dimethyl sulfide concentration in breath. Mean breath organoleptic scores.
Safety	
To assess the tolerability of an experimental dentifrice containing 0.454% stannous fluoride and 0.3% zinc chloride	Treatment emergent adverse events

This study will be considered successful if the experimental dentifrice containing stannous fluoride and zinc chloride demonstrates statistically significant greater reduction in total breath VSC compared to the reference dentifrice following 3 weeks of twice daily brushing.

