12 STATISTICAL CONSIDERATIONS AND DATA ANALYSES

12.1 Sample Size Determination

Sufficient subjects will be enrolled to randomize approximately 106 subjects to have at least 100 complete the study (at least 50 subjects per treatment arm). It is considered sufficient to have 100 subjects complete in this study to meet the study's objectives. The subjects will be stratified by their sex prior to randomization.

Existing GSKCH studies were referred to for information and data to enable calculation of an appropriate power and sample size however no relevant information was observed for a 3-week study in a gingivitis population as planned for this study.

Data from a published study that evaluated halitosis in subjects with gingivitis and periodontitis ([Pham et al., 2011](#)) was taken into consideration to provide information regarding the variability and sample size for this endpoint. The sample size in this literature was N=116 for the gingivitis population and the variability estimate was observed to be 0.46 for the organoleptic score. The scoring was on a 5-point scale with very similar descriptors to those to be used in this study however only one assessor was used for organoleptic score assessment (as opposed to 3

assessors which will be used in this study). Considering the number of assessors in this study, the standard deviation was estimated to be 0.265 (0.46/sqrt(3)).

Using the standard deviation of 0.265, for 50 subjects per arm (100 subjects completing the study) the detectable mean difference is estimated to be 0.15 for 80% power and alpha=0.05.

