12.3.1 Primary Analysis

The mean breath organoleptic score at a visit / time point will be derived across all of the recorded organoleptic scores recorded at the visit / time point.

The primary endpoint for the study is the change in mean breath organoleptic score from Baseline (pre-brushing) to 3 weeks (pre-brushing) and the comparison between the Experimental and Reference Dentifrices in the mITT population. This will be assessed at the two-sided 5% significance level.

An ANCOVA model will be used to analyze the change in mean breath organoleptic score from Baseline (pre-brushing) to 3 weeks (pre-brushing) with study product and gender as fixed effects and the mean Baseline (pre-brushing) breath organoleptic score as a covariate. The least square means for each study product will be presented based on observed margins and used to test for < 0 change from baseline. The difference between least square means for the

Experimental Dentifrice compared to the Reference Dentifrice will be presented and used to test for a difference between products. The two-sided p-values and 95% confidence intervals will be provided.

The assumption of normality and homogeneity of variance in the ANCOVA will be investigated. In case of violation of these assumptions, a suitable nonparametric test (adjusted for gender) will be performed, and results will be provided to support the ANCOVA results.

The mean pre-brushing breath organoleptic score values across the study and change from baseline will be summarised descriptively.

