12.3.2 Secondary Analyses

All secondary endpoint analyses will be performed on the mITT population. There will be no adjustment for multiplicity in the analyses described in this section.

Volatile Sulfur Compounds (VSC)

There will be individual evaluations of hydrogen sulfide, methanethiol and dimethyl sulfide concentrations in breath taken at each visit (Baseline and Week 3) at each time point (pre-brushing /1-hour post- brushing). The Total VSC at a visit/time point will have two samples. This will be derived as the sum of the hydrogen sulfide, methanethiol and dimethyl sulfide concentrations in breath and then the mean over two samples to derive one value used for analysis per visit/timepoint. The sum and the average will be performed on the raw scale and final value will be transformed.

For each concentration (hydrogen sulfide, methanethiol, dimethyl sulfide, Total VSC), the result will be log (base 10) transformed. Details of handling zero values will be detailed in the SAP.

The ANCOVA models described below will be applied for each of the mean concentrations using a different definition of Baseline and post-baseline as follows:

- Baseline = Baseline (pre-brushing), Post-baseline = Week 3 (pre-brushing)
- Baseline = Baseline (pre-brushing), Post-baseline = Week 3 (1-hour post-brushing)
- Baseline = Baseline (pre-brushing), Post-baseline = Baseline (1-hour post-brushing)
- Baseline = Week 3 (pre-brushing), Post-baseline = Week 3 (1-hour post-brushing)

The appropriate change from Baseline in the logged value will be analyzed for each post-baseline concentration using an ANCOVA model with study product and gender as fixed effects and the respective logged mean Baseline concentration as a covariate. The least square means for each study product will be based on observed margins to test for < 0 change (on the logged scale) from baseline. The difference between least square means for the Experimental Dentifrice compared to the Reference Dentifrice will be used to test for a difference between products. As well as presenting the least square means and differences on the log scale, the corresponding back transformed values (antilog base 10) will be presented to represent percent reduction from baseline and percent difference from control relative to baseline. The two-sided p-values and 95% confidence intervals (logged and back-transformed) will be provided.

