4.4.2 Secondary Efficacy Variables

All secondary endpoint analyses will be performed on the mITT population. There will be no adjustment for multiplicity in the analyses described in this section.

Secondary efficacy endpoints are:

- Mean total VSC concentration in breath.
- Mean hydrogen sulfide, methanethiol and dimethyl sulfide concentration in breath.
- Mean breath organoleptic scores.

Secondary efficacy variables are defined as:

- Change from baseline (pre-brushing) to 3 weeks (pre-brushing) in mean total VSC concentration in breath.

- Change from baseline (pre-brushing) to 3 weeks (pre-brushing) in mean hydrogen sulfide, methanethiol and dimethyl sulfide concentration in breath.
- Change from baseline (pre-brushing) to 3 weeks (1 hour post-brushing) in mean total VSC concentration in breath.
- Change from baseline (pre-brushing) to 3 weeks (1 hour post-brushing) in mean hydrogen sulfide, methanethiol and dimethyl sulfide concentration in breath.
- Change from baseline (pre-brushing) to 3 weeks (1 hour post-brushing) in mean breath organoleptic scores.
- Change from pre-brushing to 1 hour post brushing at Baseline and after 3 weeks in mean total VSC concentration in breath.
- Change from pre-brushing to 1 hour post brushing at Baseline and after 3 weeks in mean hydrogen sulfide, methanethiol and dimethyl sulfide concentration in breath.
- Change from pre-brushing to 1 hour post brushing at Baseline and after 3 weeks in mean breath organoleptic scores.

4.4.2.1 Secondary Efficacy Variable 1

Mouth air VSC determination will be performed pre- and 1 hour (± 5 minutes) post-brushing at Visits 2&3. The mouth air sample will be evaluated using the OralChroma Halitosis Measuring instrument (Model CHM-2 [Nissha FIS, Inc.; Osaka, Japan]) in agreement with the manufacturer's instructions. The OralChroma is a portable gas chromatograph with a highly sensitive semiconductor gas detector which can determine the concentration of the 3 main VSCs in breath (hydrogen sulfide, methane thiol and dimethyl sulfide).

There will be individual evaluations of hydrogen sulfide, methanethiol and dimethyl sulfide concentrations in breath taken at each visit (Baseline and Week 3) at each time point (pre-brushing /1-hour post-brushing).

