4.6 Analysis of Other Variables

Not applicable.

5 Changes to the Protocol Defined Statistical Analysis Plan

There were no changes or deviations to the originally planned statistical analysis specified in the protocol (Dated: 17/SEP/2022).

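### Study success is defined on total breath VSC, a secondary endpoint with no power calculation, while the only primary endpoint and the sample size concern the organoleptic score

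*Protocol*

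**What the plan says.** Protocol Table 3-1 and the SAP section 1.2 objectives table each list one primary endpoint, the organoleptic score, and place total VSC among the secondary endpoints. Protocol section 12.3.1 confirms it: "The primary endpoint for the study is the change in mean breath organoleptic score from Baseline (pre-brushing) to 3 weeks (pre-brushing"), with the level set by "This will be assessed at the two-sided 5% significance level". SAP sections 4.4.1.1 and 4.4.1.2 agree.

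The sentence directly after the objectives table, identical in the two documents, makes success depend on whether the experimental product "demonstrates statistically significant greater reduction in total breath VSC compared to the reference dentifrice following 3 weeks of twice daily brushing". It does not mention the organoleptic score. I found no other success criterion in either document.

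The SAP's list of secondary efficacy variables (section 4.4.2) includes "Change from baseline (pre-brushing) to 3 weeks (pre-brushing) in mean total VSC concentration in breath". For the secondary analyses, Protocol section 12.3.2 says: "There will be no adjustment for multiplicity in the analyses described in this section". The synopsis and SAP section 4.4.2 say the same.

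The sample size sections (Protocol 12.1, SAP 1.4) use organoleptic variability only, and conclude that "the detectable mean difference is estimated to be 0.15 for 80% power and alpha=0.05". SAP section 5 states: "There were no changes or deviations to the originally planned statistical analysis specified in the protocol". The SAP therefore carries the protocol's success rule forward unchanged.

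**The concern.** Read literally, the primary test plays no part in deciding whether the study succeeded. A significant organoleptic result with a non-significant VSC result is a study that met its primary endpoint and was not successful. The opposite pattern is a successful study whose primary endpoint failed. The plan does not say which statement prevails.

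The protocol itself gives reasons why the two measures could part. Section 2 says that the nose does not respond linearly to odor concentration, that product flavors complicate scoring, that VSC is a surrogate, and that non-sulfur compounds also contribute to malodor. Section 4.2 says the two dentifrices differ in flavor. Sections 2.2 and 2.4 say zinc reacts chemically with VSCs.

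The success sentence also names no contrast. Total VSC at Week 3 is compared with Day 0 both before brushing and 1 hour after brushing, and a third model uses Week 3 pre-brushing as its baseline. The pre-brushing change from Day 0 to Week 3 is the natural reading, but it is not stated.

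**Working it through.** **1. The plan's own sizing, and what it covers.** Inputs from Protocol 12.1: single-assessor variability 0.46, three assessors, 50 completers per arm, 80% power, alpha 0.05. I take alpha as two-sided, as in 12.1's companion section 12.3.1.

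- SD: 0.46/√3 = 0.2656 (stated 0.265).
- Detectable difference, normal approximation: (1.960 + 0.842) × 0.265 × √(2/50) = 0.1485. With the t distribution it is 0.1500 (stated 0.15).
- Power at 0.15: 0.15/(0.265 × 0.2) = 2.830, and Φ(2.830 − 1.960) = 80.8%. With the noncentral t it is 80.0%.

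The stated figure reproduces, but it applies to the organoleptic score only.

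**2. What the same sample size gives for VSC.** VSC is analysed on the log10 scale and no SD or target effect is given, so its power cannot be calculated from the documents. For illustration, with assumed log10 SDs and 50 per arm:

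- Detectable log10 difference d = 2.802 × SD × 0.2.
- Detectable reduction relative to control = 1 − 10^(−d).
- Power for an assumed 30% relative reduction (0.155 on the log10 scale) = Φ(0.155/(SD × 0.2) − 1.960).

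| Assumed log10 SD | Detectable reduction, 80% power | Power for a 30% reduction |
|---|---|---|
| 0.2 | 22.7% | 97% |
| 0.3 | 32.1% | 73% |
| 0.4 | 40.3% | 49% |
| 0.5 | 47.5% | 34% |
| 0.6 | 53.9% | 25% |

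**3. How often the two verdicts differ.** Treat the two test statistics as bivariate normal with correlation r. A test is met when Z > 1.96 in favor of the experimental product. The mean of Z is 2.80 for 80% power, 1.96 for 50% power and 0 for no effect. Then

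- P(success, primary not met) = P(VSC met) − P(both met);
- P(primary met, no success) = P(primary met) − P(both met).

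At r = 0 with 80% power for both, P(both met) = 0.80 × 0.80 = 0.64, so each discordant outcome has probability 0.80 − 0.64 = 0.16. All powers and correlations below are assumptions.

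| Scenario and outcome | r = 0 | 0.3 | 0.5 | 0.7 | 0.9 |
|---|---|---|---|---|---|
| Both 80%: each direction | 16.0% | 13.4% | 11.3% | 8.7% | 5.0% |
| Primary 80%, VSC 50%: primary met, no success | 40.0% | 36.6% | 34.4% | 32.1% | 30.2% |
| Primary 80%, VSC 50%: success, primary not met | 10.0% | 6.6% | 4.4% | 2.1% | 0.2% |
| No organoleptic effect, VSC 80%: success, primary not met | 78.0% | 77.6% | 77.5% | 77.5% | 77.5% |

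With 80% power for both, total disagreement is twice the first row: 32% at r = 0 down to 10% at r = 0.9.

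**The case against.** The strongest reply is that the success sentence is a label. It appears once in each document, and not in the synopsis or the analysis sections. No model, population, table or stopping rule depends on it. A statistician following Protocol 12.3.1 and SAP 4.4.1.2 would report the primary result correctly. That is true, and it limits the problem to the declaration of success. It does not remove it, because this is the only success rule in the documents.

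The magnitudes rest on assumption. Protocol sections 2 and 4.2 cite correlation between VSC and organoleptic measures, which makes r = 0 the least plausible column, although correlation between measurements is not correlation between treatment-effect tests. The 78% figure is nearly arithmetic (0.80 × 0.975 at r = 0) and assumes a VSC effect with no organoleptic effect. These figures illustrate the contradiction; they do not estimate what this trial will show.

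A secondary endpoint needs no power calculation of its own. That is also right: its absence matters only because the success sentence lets VSC decide.

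On error rates, one named VSC contrast would keep its own 5% two-sided error (2.5% in the favorable direction), so inflation is not the main complaint. That reassurance holds only once the contrast is named. If a favorable result on either of two Week 3 contrasts were allowed to count, the favorable error under independence would be 1 − 0.975² = 4.9%.

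**Conclusion.** The concern holds. It follows from the text alone: both documents tie success to a secondary endpoint, while the only primary endpoint and the only sample size basis are the organoleptic score, and nothing in either document reconciles them. The consequence is a headline conclusion that can contradict the primary test and that rests on a variable the trial was not sized for. Planned estimates and p-values stand.

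The frequency of contradiction depends on VSC power and on the correlation between the tests, neither of which the documents give. At an illustrative 80% power for both and correlation 0.5, the verdicts differ in 22.6% of trials (11.3% in each direction). Lower VSC power makes a met primary without success the more common conflict. This must be corrected before unblinding, because a choice between the two endpoints made afterwards would look data-driven.

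**What to change.** Amend the sentence after Table 3-1 in Protocol section 3 and its copy in SAP section 1.2 together, before unblinding. Success should mean a statistically significant greater reduction, for the experimental product, in mean organoleptic score from Day 0 to Week 3, both before brushing. This agrees with the stated primary endpoint and leaves the sample size as it is.

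The new sentence should also say which test decides. Protocol 12.3.1 uses the nonparametric test only in support of the ANCOVA, while SAP 4.4.1.2 lets it prevail if the two disagree. That is a separate inconsistency, but the amended success rule would inherit it.

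If a VSC claim is also wanted, name the contrast (total VSC, Day 0 pre-brushing to Week 3 pre-brushing) and test it second, at two-sided 5%, only if the primary is significant. The no-multiplicity statements in the Protocol synopsis, Protocol 12.3.2 and SAP 4.4.2 then need matching edits. If the sponsor really intends VSC to decide, make it primary or co-primary with its own SD, effect size and power.

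**Cost.** The base change is one sentence per document, with no new subjects or data; as a protocol amendment it needs prior IRB/EC approval under Protocol 13.3.1. The fixed sequence adds three small edits. The VSC-primary or co-primary route needs a new power calculation and perhaps a different sample size. The price of the base change is that VSC cannot carry a success claim if the primary test fails.
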